7. INVESTIGATIONAL PLAN

7.1. Overall Study Design

This two-part study is designed to characterize the steady-state PK of oral tazemetostat and its metabolite EPZ 6930 when administered as a single and twice daily dose in subjects with advanced malignancies while taken alone or in combination with either itraconazole or rifampin (Figure 1).

Part 1: Tazemetostat and Itraconazole Drug Interaction

Part 1 of the study will evaluate the drug-drug interaction between tazemetostat and itraconazole in an open-label, fixed sequential cross over design (Figure 2).

A screening visit will occur within 30 days of signing an informed consent form (ICF). During the screening phase, subjects will be evaluated for eligibility to participate in the study. Subjects who meet the protocol criteria may be admitted in the evening to the clinical study center, or visit the clinic if staying locally, on day -1. For Cycle 1, subjects may be admitted to the clinical study center during PK sampling periods or must agree to stay locally with frequent clinic visits as required and, optional admission to the center, if available. Prior to dosing on day 1 of Cycle 1, subject eligibility will be reconfirmed. On day 1, a single oral dose of 400 mg tazemetostat will be administered in the morning (eg, 7 – 9 am) followed by 2 days of multiple blood sampling (day 1 – 3). From day 3 – 14, subjects will receive an oral 400 mg dose of tazemetostat twice daily (12 hours apart, once in the morning [eg, 7 – 9 am] and once in the evening [eg, 7 – 9 pm]). In the evening of day 14, subjects may be admitted to the clinical study center. On day 15, a single oral dose of 400 mg tazemetostat will be administered in the morning (eg, 7 – 9 am) followed by 3 days of multiple blood sampling (day 15 – 18). From day 18 – 20, a single dose of oral 200 mg itraconazole will be administered daily in the morning (eg, 7 – 9 am) after a meal. In the evening of day 20, subjects may be admitted to the clinical study unit. From day 21 – 35, subjects will receive an oral 400 mg dose of tazemetostat twice daily, once in the morning (eg, 7 – 9 am) and once in the evening (eg, 7 – 9 pm), co-administered in the morning (eg, 7 – 9 am) after a meal with a single dose of oral 200 mg itraconazole followed by 1 day of multiple blood sampling (day 21 – 22). In the evening of day 35, subjects may be admitted to the clinical study center. On day 36, subjects will receive a single oral dose of 400 mg tazemetostat co-administered in the morning (eg, 7 – 9 am) after a meal with a single dose of oral 200 mg itraconazole followed by 3 days of multiple blood sampling (day 36 – 39). Itraconazole will also be administered on day 37 and 38 as a single oral 200 mg daily dose in the morning (eg, 7 – 9 am) after a meal. **Note:** Tazemetostat will not be administered on day 37 and 38. After the 72-hour PK sample collection, safety assessments will be conducted on day 39. Sparse PK samples will be collected pre-dose (0 hour) and 2 hours post-dose on day 25, 28, 31, and 34.

Subjects may discontinue from the study after completion of Cycle 1 or can continue treatment (Cycle 2+ onwards) until Investigator-assessed clinical progression per standard practice, or unacceptable toxicity, or until another discontinuation criterion is met. For subjects continuing tazemetostat treatment at the recommended therapeutic dose (oral 800 mg tazemetostat twice daily [12 hours apart]), Cycle 2 will begin on day 40 (Cycle 2 Day 1) and each subsequent cycle from Cycle 2+ onwards will be of 28-day duration. Safety and tolerability will be assessed throughout the subject's participation. Subjects will be instructed to report any adverse events

that occur up to 30 days after the last dose of tazemetostat. Subjects must have an end of study visit 30 days after the last dose of tazemetostat for safety assessment.

Part 2: Tazemetostat and Rifampin Drug Interaction

Part 2 of the study will evaluate the drug-drug interaction between tazemetostat and rifampin in an open-label, fixed sequential cross over design (Figure 3).

A screening visit will occur within 30 days of signing an informed consent form (ICF). During the screening phase, subjects will be evaluated for eligibility to participate in the study. Subjects who meet the protocol criteria may be admitted in the evening to the clinical study center, or visit the clinic if staying locally, on day -1. For Cycle 1 subjects may be admitted to the clinical study center during PK sampling periods or must agree to stay locally with frequent clinic visits as required and optional admission to the center if available. Prior to dosing on day 1 of Cycle 1, subject eligibility will be reconfirmed. On day 1, a single oral dose of 800 mg tazemetostat will be administered in the morning (eg, 7 – 9 am) followed by 2 days of multiple blood sampling (day 1 – 3). From day 3 – 14, subjects will receive an oral 800 mg dose of tazemetostat twice daily (12 hours apart once in the morning [eg, 7 – 9 am] and once in the evening [eg, 7 – 9 pm]). In the evening of day 14, subjects may be admitted to the clinical study center. On day 15, a single oral dose of 800 mg tazemetostat will be administered in the morning (eg, 7 – 9 am) followed by 2 days of multiple blood sampling (day 15 – 17). From day 17 – 23, subjects will receive an oral 800 mg dose of tazemetostat twice daily, once in the morning (eg, 7 – 9 am) and once in the evening (eg, 7 – 9 pm), co-administered in the morning (eg, 7 – 9 am) one hour before a meal with a single dose of oral 600 mg rifampin. In the evening of day 23, subjects may be admitted to the clinical study center. On day 24, subjects will receive a single oral dose of 800 mg tazemetostat co-administered in the morning (eg, 7 – 9 am) one hour before a meal with a single dose of oral 600 mg rifampin followed by 2 days of multiple blood sampling (day 24 – 26). Rifampin will also be administered on day 25 as a single oral 600 mg dose in the morning (eg, 7 – 9 am) one hour before a meal. **Note:** Tazemetostat will not be administered on day 25. After the 48-hour PK sample collection, safety assessments will be conducted on day 26. Sparse PK samples will be collected pre-dose (0 hour) and 2 hours post-dose on day 19 and 21.

Subjects may discontinue from the study after completion of Cycle 1 or can continue treatment (Cycle 2+ onwards) until Investigator-assessed clinical progression per standard practice, or unacceptable toxicity, or until another discontinuation criterion is met. For subjects continuing tazemetostat treatment at the recommended therapeutic dose (800 mg tazemetostat twice daily [12 hours apart]), Cycle 2 will begin on day 27 (Cycle 2 Day 1) and each subsequent cycle from Cycle 2+ onwards will be of 28-day duration. Safety and tolerability will be assessed throughout the subject's participation. Subjects will be instructed to report any adverse events that occur up to 30 days after the last dose of tazemetostat. Subjects must have an end of study visit 30 days after the last dose of tazemetostat for safety assessment.

Rollover Study

All subjects who receive the recommended therapeutic dose of 800 mg tazemetostat twice daily [12 hours apart] for 9 Cycles or longer, and are eligible to continue receiving tazemetostat, will transfer to a Rollover Study CC1 for monitoring and continued study drug at the Investigator and Medical Monitor's discretion.

7.2. Number of Subjects

Approximately 40 subjects will be enrolled in the study assuming about a 40% drop out rate to achieve 12 subjects who complete each part of the study for a total of 24 completed subjects. Subjects will complete either Part 1 or Part 2, but not both.

Subjects who require a tazemetostat dose interruption or reduction during Cycle 1 of either Part 1 or Part 2 will be replaced. During Cycle 1, subjects who miss two or more consecutive tazemetostat/itraconazole/rifampin doses or more than three tazemetostat/itraconazole/rifampin doses in total will be replaced. Subjects who miss two or more consecutive PK blood sample collections during either part of Cycle 1 will be replaced. Subjects that require replacement will be discontinued from study treatment.

7.3. Treatment Assignment

After obtaining written, informed consent, subjects with advanced malignancies will be screened according to the exclusion and inclusion criteria. Subjects who have complied with all selection criteria will receive a unique subject number upon enrollment in the study. Subject numbers will be allocated sequentially in the order in which subjects are enrolled. The Investigator or designee will enter the corresponding subject number and complete each eCRF.

Subjects will be assigned to the study as follows:

Part 1: Tazemetostat and Itraconazole Drug Interaction ([Figure 2](#))

Part 2: Tazemetostat and Rifampin Drug Interaction ([Figure 3](#))

Part 1: Tazemetostat and Itraconazole Drug Interaction

Subjects in Part 1 of the study will receive a single oral, 400 mg dose of tazemetostat on Day 1, 15, and Day 36. The subjects will receive tazemetostat (oral 400 mg dose) tablets to be taken twice daily from Day 3 – 14 and Day 21 – 35. In addition, the subjects will receive oral 200 mg itraconazole once daily from Day 18 – 38. Detailed schedule of assessments is provided in [Table 3](#).

Note: Subjects will not be dosed with tazemetostat on day 2, from day 16 – 20, 37, and 38.

Part 2: Tazemetostat and Rifampin Drug Interaction

Subjects in Part 2 of the study will receive a single, oral, 800 mg dose of tazemetostat on Day 1, 15 and Day 24. The subjects will receive tazemetostat (oral 800 mg dose) tablets to be taken twice daily from Day 3 – 14 and Day 17 – 23. In addition, the subjects will receive oral 600 mg rifampin once daily from Day 17 – 25. Detailed schedule of assessments is provided in [Table 4](#).

Note: Subjects will not be dosed with tazemetostat on day 2, 16, and 25.

7.4. Restrictions During Study Treatment

Subjects will abstain from ingesting Seville oranges, grapefruit or grapefruit juice, and foods/beverages that contain those, for 24 hours prior to the first dose of study treatment until the last dose of study treatment.

Subjects should avoid prolonged exposure to sunlight while receiving study treatment. In addition, subjects should take other measures to avoid ultraviolet exposure including tanning beds. Use sunscreen, sunglasses, and protective clothing whenever outside.

7.5. Dose Adjustment Criteria

7.5.1. Dose Modification

Tazemetostat dose interruptions and reductions will not be allowed in Cycle 1 (both Part 1 and Part 2). Dose modification only applies to Cycle 2 and beyond. If a dose interruption or reduction is required during Cycle 1, the subject will be discontinued from study treatment and replaced. For Cycle 2 and beyond, an interruption in the administration of tazemetostat for more than 14 days must be discussed with the Medical Monitor before treatment can be resumed. Dose-limiting toxicities are covered in [Section 7.5.2](#).

Toxicity will be managed by concomitant medication (as appropriate), treatment interruption, dose reduction, and treatment discontinuation, or a combination of these. During treatment with tazemetostat, dose interruption and reduction for subjects who experience tazemetostat-related toxicity will be in accordance with the instructions in [Table 2](#). If a case of adult T-LBL/T-ALL occurs enrollment will be suspended, and the benefit-risk of the drug will be assessed by the Tazemetostat Safety Committee and will be communicated to all Health Authorities and Ethics Committees. For any MDS/AML or other myeloid malignancies like MPN, tazemetostat will be discontinued.

For subjects who require dose interruption due to tazemetostat-related toxicity after Cycle 1 of the study, the treatment may re-start once the toxicity has been resolved to Grade ≤ 1 or baseline, unless otherwise noted, according to the instructions in [Table 2](#).

For continuation of treatment for Cycle 2 and beyond, subjects must meet the following retreatment criteria:

- Platelet count must be $\geq 75 \times 10^9/L$
- Absolute neutrophil count (ANC) must be $\geq 1,000/mm^3$ ($\geq 1.0 \times 10^9/L$) for hematologic malignancy subjects and ANC must be $\geq 1,500/mm^3$ ($\geq 1.5 \times 10^9/L$) for solid tumor subjects.
- Any Grade 3 or higher toxicity must have resolved to at least Grade 1 or baseline, unless otherwise noted.

7.5.2. Dose Modification due to Treatment-Related Toxicity

In Cycle 2 and beyond for tazemetostat, other toxicities that, in the opinion of the Investigator are possibly, probably, or definitely related to study treatment, should be managed per [Table 2](#). Toxicities that are felt by the Investigator to be unrelated to tazemetostat but clinically significant should be discussed with the Medical Monitor. In the event of an urgent unrelated toxicity, study treatment should be interrupted as per [Table 2](#). Dose re-escalation is not permitted.

Table 2: Dose Modifications for Tazemetostat Treatment-Related Toxicities (Cycle 2+)

Toxicity	During Therapy	Approximate Dose Adjustment
Grade 1		
All occurrences	Continue tazemetostat	Maintain dose level
Grade 2^{c, d}		
1st occurrence	Interrupt tazemetostat until resolved to Grade \leq 1 or baseline ^b	Maintain dose level
2nd occurrence (same or new toxicity)		Restart at 600 mg twice daily
3rd occurrence (same or new toxicity)		Restart at 400 mg twice daily
4th occurrence (same or new toxicity)		Discuss with Medical Monitor
Grade 3^c (Not Including Neutropenia and Thrombocytopenia)		
1st occurrence	Interrupt tazemetostat until resolved to Grade \leq 1 or baseline ^b	Restart at 600 mg twice daily
2nd occurrence (same or new toxicity)		Restart at 400 mg twice daily
3rd occurrence (same or new toxicity)	Discontinue tazemetostat	Not applicable
Grade 3 Neutropenia (ANC: $<1.0 - 0.5 \times 10^9/L$)		
ANC $< 1.0 \times 10^9/L$ 1st occurrence	Interrupt tazemetostat until resolved to ANC $\geq 1.0 \times 10^9/L$ ^b	Maintain dose level
2nd occurrence		Restart at 600 mg twice daily
3rd occurrence		Restart at 400 mg twice daily
4th occurrence	Discontinue tazemetostat	Not applicable
Grade 3 Thrombocytopenia		
1st occurrence	Interrupt tazemetostat until resolved to Grade \leq 1 or baseline ^b	Restart at 600 mg twice daily
2nd occurrence		Restart at 400 mg twice daily
3rd occurrence	Discontinue tazemetostat	Not applicable
Grade 4		
1st occurrence	Interrupt tazemetostat until resolved to Grade \leq 1 or baseline ^b	Restart at 600 mg twice daily
2nd occurrence (same or new toxicity)	Discontinue tazemetostat	Not applicable

Abbreviations: ANC = absolute neutrophil count

^a Excluding alopecia and nausea, vomiting or diarrhea not receiving adequate treatment.

^b An interruption of tazemetostat for more than 14 days due to any toxicity must be discussed with the Medical Monitor before treatment can be resumed

^c Excluding Grade 2 and 3 anemia: subjects are allowed to continue tazemetostat at their current dose level with transfusion per Investigator discretion

^d Excluding Grade 2 neutropenia and thrombocytopenia

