7.5.3. Continuation of Treatment

After successful completion of Cycle 1 (both Part 1 and Part 2), subjects who have not experienced unacceptable toxicity and have no signs or symptoms of progressive disease per standard practice may continue treatment (Cycle 2+ onwards) with tazemetostat at the recommended therapeutic dose (oral 800 mg tazemetostat twice daily [12 hours apart]) until Investigator-assessed clinical disease progression, unacceptable toxicity, withdrawal of consent, or termination of the study by the Sponsor.

Subjects who experience clinical progression at the end of Cycle 1, as assessed by Investigator per current standards of care in the absence of clinical deterioration, may be permitted to continue study treatment (Cycle 2 and beyond) if the subject is receiving clinical benefit in the opinion of the Investigator. In the event of such a situation, the Investigator must contact the Medical Monitor to discuss the assessment of risk:benefit of maintaining the subject on study.

All subjects who receive the recommended therapeutic dose of 800 mg tazemetostat twice daily (12 hours apart) for 9 Cycles or longer, and are eligible to continue receiving tazemetostat, will transfer to a Rollover Study **CCI** for monitoring and continued study drug at the Investigator and Medical Monitor's discretion.

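### Table 2's fixed restart doses can direct a rise from 400 to 600 mg twice daily that Section 7.5.2 forbids, and the rule for counting occurrences is not stated

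*Protocol*

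**What the plan says.** Four statements in the protocol bear on this.

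- **The ban.** Section 7.5.2, in the paragraph just above Table 2, says without exception: "Dose re-escalation is not permitted".
- **The status of the table.** Section 7.5.1 makes Table 2 the governing instruction: "dose interruption and reduction for subjects who experience tazemetostat-related toxicity will be in accordance with the instructions in" that table. It also sets the scope: "Dose modification only applies to Cycle 2 and beyond".
- **The starting dose.** Under Section 7.5.3, subjects who complete Cycle 1 go on at 800 mg twice daily, in both parts.
- **The table cells.** Table 2 has five blocks that change dosing: Grade 2, Grade 3 (leaving out neutropenia and thrombocytopenia), Grade 3 neutropenia, Grade 3 thrombocytopenia, and Grade 4. Each block begins again at a first occurrence. The dose-reduction cells read either "Restart at 600 mg twice daily" or "Restart at 400 mg twice daily", with no condition on the dose the subject is taking when the event occurs.

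Footnotes b, c and d cover long interruptions, anemia, and Grade 2 neutropenia and thrombocytopenia. None ties the restart dose to the current dose or says how occurrences add up across blocks. The SAP does not address the question.

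**The concern.** Sites apply a dose-modification table by finding the row that matches the event. A subject who has been reduced to 400 mg twice daily under one block and then has a first event in another can land on a row that names 600 mg. Followed literally, that row raises the dose after a further toxicity, possibly one of Grade 4. The sentence above the table says this must not happen, so the site cannot follow both.

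At stake is whether an individual subject with repeated toxicity has a clear instruction. The estimate of the drug interaction is not at stake.

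**Working it through.** No statistical formula applies. The check is to trace Table 2 as printed.

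**Inputs.** Start at 800 mg twice daily (Section 7.5.3). Count occurrences separately within each block, an assumption drawn from the numbering restarting under each heading. The actions in Table 2, with doses in mg twice daily, are:

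| Block | 1st | 2nd | 3rd | 4th |
|---|---|---|---|---|
| Grade 2 | same dose | 600 | 400 | discuss with Medical Monitor |
| Grade 3, general | 600 | 400 | discontinue | – |
| Grade 3 neutropenia | same dose | 600 | 400 | discontinue |
| Grade 3 thrombocytopenia | 600 | 400 | discontinue | – |
| Grade 4 | 600 | discontinue | – | – |

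**Step 1: two events.** There are 5 × 5 = 25 ordered sequences. No block names 400 mg at a first occurrence, so nobody is at 400 mg after one event and the second cannot raise the dose: 0 of 25.

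**Step 2: three events.** Of the 25 two-event sequences only Grade 4 followed by Grade 4 has ended in discontinuation, so 24 continue and 24 × 5 = 120 three-event sequences are possible. A subject is at 400 mg after two events only by two general Grade 3 events or two Grade 3 thrombocytopenia events. The third event then raises the dose in these cases:

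- Grade 3, Grade 3, first Grade 3 thrombocytopenia: 800 → 600 → 400 → 600
- Grade 3, Grade 3, first Grade 4: 800 → 600 → 400 → 600
- Grade 3 thrombocytopenia twice, first general Grade 3: 800 → 600 → 400 → 600
- Grade 3 thrombocytopenia twice, first Grade 4: 800 → 600 → 400 → 600

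That is 4 of 120. Each rise is 600 − 400 = 200 mg per dose, and 200/400 = 50%.

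**Step 3: the other cells.** Two more cells name 600 mg: second Grade 2 and second Grade 3 neutropenia. Each can be reached from 400 mg in four events, for example one Grade 2, two general Grade 3, then a second Grade 2. All five 600 mg cells can therefore conflict with the ban.

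**Step 4: alternative readings.** Take a subject at 400 mg after two general Grade 3 events whose third event is a first Grade 4 or first Grade 3 thrombocytopenia event.

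| Reading | Resulting instruction |
|---|---|
| Count within block, follow the table | restart at 600 mg twice daily |
| Count within block, ban overrides the table | no restart dose stated |
| Count across blocks | third event: discontinue in the thrombocytopenia block; past the last Grade 4 row, which is discontinue |

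The three readings lead to three different actions.

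**The case against.** The best defence is that the protocol already prevents the harmful outcome. The ban is unconditional and sits directly above the table, so a site that reads the whole section would not move a subject from 400 to 600 mg. Section 7.5.3 allows treatment to end for unacceptable toxicity, and footnote b sends interruptions of more than 14 days to the Medical Monitor. This has force: a reader might infer that the protocol simply orders a dose increase after a Grade 4 event, and the documents do not support that, because the same section forbids it. But letting the ban prevail only removes the 600 mg instruction. It puts nothing in its place.

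A second objection is that separate counting is nowhere stated. That is correct. The Grade 2, general Grade 3 and Grade 4 blocks label later rows in the style of "2nd occurrence (same or new toxicity"), which could be read as pooling more widely than one block. Within-block counting is the natural reading, not a stated rule, and the missing rule is part of the problem.

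Third, the situation is uncommon. It needs at least three dose-modifying events in one subject during optional treatment, in a study planned for 24 completers. Section 5.5.1 reports that the events most often leading to dose reduction did so in fewer than 1% of adults. This stands, and it limits the weight of the point.

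Two further inferences are tempting and should not be drawn. A subject at 600 mg who meets a 600 mg cell has an unchanged dose; that is not re-escalation and contradicts nothing. Nor are the tolerability summaries materially distorted. SAP Section 14.1 counts subjects with reductions or interruptions, and in all four three-event paths the subject already has two of each. At most the classification of the later event changes.

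**Conclusion.** The inconsistency is real but narrow. On within-block counting, Table 2 directs a rise from 400 to 600 mg twice daily in 4 of 120 three-event paths, against the ban in the same section. The fraction describes the table's structure and says nothing about how often such a subject will occur.

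The conclusion rests on two things: that numbering which restarts under each heading means separate counts, and that the 400 and 600 mg cells mean what they print. If the first assumption fails, the outcome moves to discontinuation. If the ban is given priority, no action is stated. No text in either document chooses among these.

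The effect is confined to Cycle 2 onwards. In Cycle 1 a subject needing an interruption or reduction is discontinued and replaced (Section 7.5.1), so the primary PK comparison is unaffected. This is a safety-relevant wording fault to correct, not a threat to the study's conclusions.

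**What to change.** Reconcile Table 2 with the re-escalation sentence in Section 7.5.2. The revised text should state:

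1. whether occurrences are counted within each block or across blocks; and
2. what applies when a subject is already at or below the dose that a row names.

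The sponsor's clinical team decides the content of both; this review proposes no dose or rule.

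The cost is a wording change to one table and its footnotes at the next amendment, with the usual ethics re-approval. It needs no new assessments, no change in sample size and no change to the PK analysis.
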